Biopsy specimens per subject should be obtained by endoscopy for histologic assessment at the time points indicated in [Appendix C](#) and [Appendix E](#). Using routine forceps for tissue collection, obtain the required number of biopsy specimens and process the specimens following the instructions in the study-specific laboratory manual.

Intestinal Tissue Analysis

The following analyses will be sent to the central laboratory and performed on tissue samples:

1. Qualitative UC histological assessment using Geboes histologic activity score,²⁵ and other histologic scoring systems. These samples may not be read in real time, however if unexpected findings, such as dysplasia, are noted on the histology biopsies, the central laboratory will contact the investigator to inform him/her about the unexpected finding. Subjects who are found to have high grade colonic dysplasia on the submitted biopsy will be terminated from the trial at the time the dysplasia is discovered. Unexpected findings should be recorded as an adverse event.
2. Subjects will have the option to provide tissue biopsies (per local requirements) for future exploratory research and/or validation studies. For more information, please refer to Section 5.3.1.2.

COVID-19 Pandemic-Related Acceptable Protocol Modifications

Biopsy completion should follow the endoscopy guidance if the visit is affected by COVID-19. If an endoscopy is completed at an alternative location from the study site the study required biopsy is not required. Biopsy can be completed per endoscopist's discretion for local evaluation.

Follow-Up Period

Subjects will be contacted approximately 30 days after the last administration of study drug to obtain information on any new or ongoing adverse events (AEs).

During this follow-up call the results of the follow-up at home pregnancy test should be communicated to the site and follow reporting found in Section 6.1.6.

Subjects may discontinue study drug treatment at any time during study participation. Subjects that end study participation early will have a Premature Discontinuation Visit and complete the procedures outlined for the PD Visit in [Appendix C](#) through [Appendix F](#) as soon as possible after the last dose of study drug and preferably prior to the administration of any new therapies.

Unscheduled Visits

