3.0 Endpoints

The induction baseline (thereafter referred to as Baseline) visit date is the date when the first dose of study drug is received during Induction Studies. The baseline value for a variable is defined as the last non-missing value on or before the date of the first dose of study drug during Induction Studies.

The maintenance baseline visit date is on the same day as the final visit in the Induction Studies (thereafter referred to as Maintenance Baseline). The maintenance baseline value for a variable is defined as the last non-missing value on or before the date of the first dose of study drug during Maintenance Study.

The terminologies and efficacy variables are defined as below:

- Mayo Score
 - **Full Mayo Score:** composite score of UC disease activity based on the stool frequency subscore [SFS] (0 – 3), rectal bleeding subscore [RBS] (0 – 3), physician's global assessment [PGA] subscore (0 – 3) and endoscopic subscore (0 – 3). This score ranges from 0 – 12 points with higher scores representing more severe disease.
 - **Partial Mayo Score:** Full Mayo score minus the endoscopic subscore.
 - **Adapted Mayo Score:** Full Mayo score minus the PGA subscore.
 - **Partial Adapted Mayo Score:** Adapted Mayo score minus the endoscopic subscore.
- Clinical Remission
 - **per Full Mayo Score:** Full Mayo score ≤ 2 with no subscore > 1 .
 - **per Adapted Mayo Score:** Adapted Mayo score ≤ 2 , with SFS ≤ 1 and not greater than baseline, RBS of 0, and endoscopic subscore ≤ 1 .
 - **per Partial Mayo Score:** Partial Mayo score ≤ 2 , with no subscore > 1 .
- Clinical Response
 - **per Full Mayo Score:** decrease in Full Mayo score of ≥ 3 points and $\geq 30\%$ from Baseline, PLUS a decrease in RBS ≥ 1 or an absolute RBS ≤ 1 .
 - **per Adapted Mayo Score:** decrease in Adapted Mayo score ≥ 2 points and $\geq 30\%$ from Baseline, PLUS a decrease in RBS ≥ 1 or an absolute RBS ≤ 1 .
 - **per Partial Mayo Score:** decrease in Partial Mayo score ≥ 2 points and $\geq 30\%$ from Baseline, PLUS a decrease in RBS ≥ 1 or an absolute RBS ≤ 1 .

- **per Partial Adapted Mayo Score:** decrease in Partial Adapted Mayo score ≥ 1 point and $\geq 30\%$ from Baseline, PLUS a decrease in RBS ≥ 1 or an absolute RBS ≤ 1 .
- **Endoscopic Improvement:** Endoscopic subscore of 0 or 1.
- **Endoscopic Remission:** Endoscopic subscore of 0.
- **Histologic Improvement:** decrease from Baseline in Geboes score.
- **Histologic Remission:** Geboes score < 2 .

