- As Observed (AO): The AO analysis will not impute values for missing evaluations, and thus a subject who does not have an evaluation on a scheduled visit will be excluded from the AO analysis for that visit. AO will include all values collected in the study regardless the occurrence of UC-related rescue medication intercurrent event.

Details of Multiple Imputation (MI) for NRI-C and HMI: Markov Chain Monte Carlo (MCMC) will be first applied to augment data into monotonic missing pattern, where applicable, and PROC MI will be used to generate 30 datasets using the regression method. The variables to be included in the imputation model are: treatment group, stratification factors (Bio-IR status (Bio-IR or Non-Bio-IR) at the Baseline of the Induction Study, clinical remission status at Week 0 (yes or no), and corticosteroid use at Week 0 (yes or no)), Baseline measurement, and if applicable, post-baseline measurements at each visit up to the end of the analysis period. The random seed for MCMC and the random seed for PROC MI are specified in [Appendix D](#). The imputed post-baseline measurements will be rounded to the same precision as the observed data before the determination of responder status. Subjects will be characterized as responders or non-responders based on MI imputed datasets. Using the CMH model adjusted by stratification factors (Bio-IR status (Bio-IR or Non-Bio-IR) at the Baseline of the Induction Study, clinical remission status at Week 0 (yes or no), and corticosteroid use at Week 0 (yes or no)), the imputed endpoints will be analyzed using each of the 30 datasets. SAS PROC MIANALYZE will be used to generate the final treatment difference between each upadacitinib treatment group and placebo group and statistical inference of the risk difference, including hypothesis testing and 95% CI using Rubin's rule and T-distribution.³ [REDACTED]

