Appendix D. Random Seeds

In case of non-convergence, the random seed will be updated by adding 100000 at each attempt until convergence of model happens.

The missing Mayo subscores are imputed to calculate the Adapted Mayo score, Partial Mayo score, Partial Adapted Mayo score, and Full Mayo score.

Table D-1. Random Seeds for NRI-C

Endpoints	Random Seed	
	MCMC Procedure	PROC MI
Rectal bleeding subscore (0, 1, 2, 3)	31481	32061
Stool frequency subscore (0, 1, 2, 3)	31482	32062
Endoscopic subscore (0, 1, 2, 3)	31483	32063
Physician's global assessment (0, 1, 2, 3)	31484	32064
Geboes grade score (0, 1, 2, 3, 4, 5)	31485	32065
Geboes Grade 3 subscore (3.1, 3.2, 3.3)	31486	32066
No bowel urgency (0, 1)	31487	32067
No abdominal pain (0, 1, 2, 3)	31488	32068
Fecal Calprotectin (< 150 mg/kg)	31489	32069
IBDQ response and remission in domain and total score	31490	32070

Table D-2. Random Seeds for HMI

Endpoints	Random Seed	
	MCMC Procedure	PROC MI
Rectal bleeding subscore (0, 1, 2, 3)	31501	32501
Stool frequency subscore (0, 1, 2, 3)	31502	32502
Endoscopic subscore (0, 1, 2, 3)	31503	32503

Table D-3. Random Seeds for DBMI

Endpoints	Random Seed
	PROC MI
Change from Baseline in IBDQ total score	32169
Change from Baseline in FACIT-F	32170

Table D-4. Random Seeds for RTB-MI

Endpoints	Random Seed
	PROC MI
Change from Baseline in IBDQ total score	33169
Change from Baseline in FACIT-F	33170

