 - Multiple Imputation (MI) for NRI-C and HMI: Markov Chain Monte Carlo (MCMC) will be first applied to augment data into monotonic missing pattern, where applicable, and PROC MI will be used to generate 30 datasets using the regression method. The variables to be included in the imputation model are: treatment group, stratification factors (bio-IR status (bio-IR vs. non-bio-IR), Baseline corticosteroid use (yes vs. no) and Baseline Adapted Mayo score (≤ 7 vs. > 7)), Baseline measurement, and if applicable, post-baseline measurements at each visit up to the end of the analysis period. The random seed for MCMC and the random seed for PROC MI are specified in [Appendix D](#). The imputed post-baseline measurements will be rounded to the same precision as the observed data before the determination of responder status. Subjects will be characterized as responders or non-responders based on MI imputed datasets. Using the CMH model adjusted by stratification factors (bio-IR status (bio-IR vs. non-bio-IR), Baseline corticosteroid use (yes vs. no) and Baseline Adapted Mayo score (≤ 7 vs. > 7)), the imputed endpoints will be analyzed using each of the 30 datasets. SAS PROC MIANALYZE will be used to generate the final inferences of the risk difference between upadacitinib treatment group and placebo group, using Rubin's rule. 

 - As Observed (AO): The AO analysis will not impute values for missing evaluations, and thus a subject who does not have an evaluation on a scheduled
-

visit will be excluded from the AO analysis for that visit. AO will include all values collected in the study.

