Appendix D. Random Seeds

In case of non-convergence, the random seed will be updated by adding 100000 at each attempt until convergence of model happens.

The missing Mayo subscores are imputed to calculate the Adapted Mayo score, Partial Mayo score, Partial Adapted Mayo score, and Full Mayo score.

Table D-1. Random Seeds for NRI-C

Endpoints	Random Seed	
	MCMC Procedure	PROC MI
Rectal bleeding subscore (0, 1, 2, 3)	21481*	22061 [#]
Stool frequency subscore (0, 1, 2, 3)	21482	22062
Endoscopic subscore (0, 1, 2, 3)	21483	22063
Physician's global assessment (0, 1, 2, 3)	21484	22064
Geboes grade score (0, 1, 2, 3, 4, 5)	21485	22065
Geboes Grade 3 subscore (3.1, 3.2, 3.3)	21486	22066
No bowel urgency (0, 1)	21487	22067
No abdominal pain (0, 1, 2, 3)	21488	22068
Fecal Calprotectin (< 150 mg/kg)	21489	22069
IBDQ response and remission in domain and total score	21490	22070
PGIC (0, 1, 2, 3, 4, 5, 6)	21491	22071
PGIS (0, 1, 2, 3, 4, 5, 6)	21492	22072

* This is SAS numerical form of Oct 24, 2018, which is the first subject randomized in this study.

This is SAS numerical form of May 26, 2020, which is the last subject randomized in this study.

Table D-2. Random Seeds for HMI

Endpoints	Random Seed	
	MCMC Procedure	PROC MI
Rectal bleeding subscore (0, 1, 2, 3)	21501	22501
Stool frequency subscore (0, 1, 2, 3)	21502	22502
Endoscopic subscore (0, 1, 2, 3)	NA	22503

Note: The MCMC procedure is not applicable for imputation of endoscopic subscore, which is collected at Baseline and Week 8 only for the primary efficacy endpoint.

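### The Phase 3 imputation models list no same-visit companion component, so COVID-imputed composites would be met too rarely if components are correlated; the effect on the treatment difference is small and conservative

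*SAP*

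**What the plan says.** Section 8.3.1 of the Substudy 3 SAP and of the Substudy 2 SAP describe the same procedure. MCMC first makes the missing pattern monotone where needed, and regression in PROC MI then gives 30 datasets. The predictors are introduced as a list: "The variables to be included in the imputation model are: treatment group, stratification factors", followed by "Baseline measurement, and if applicable, post-baseline measurements at each visit up to the end of the analysis period". In Substudy 3 the stratification factors include "clinical remission status at Week 0 (yes or no), and corticosteroid use at Week 0 (yes or no".

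Appendix D of each SAP gives rectal bleeding (RBS), stool frequency (SFS), endoscopy, PGA and Geboes their own rows and seeds; one row, for example, is "Geboes grade score (0, 1, 2, 3, 4, 5". It explains that "The missing Mayo subscores are imputed to calculate the Adapted Mayo score, Partial Mayo score, Partial Adapted Mayo score, and Full Mayo score". Under Table D-2 the Substudy 2 SAP adds: "The MCMC procedure is not applicable for imputation of endoscopic subscore, which is collected at Baseline and Week 8 only".

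Under NRI-C only COVID-missing data are multiply imputed; other missing data count as non-response. HMI, a sensitivity analysis of the primary endpoint, uses the same imputation model.

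The protocol foresees partly observed composites. Where COVID-19 prevents the Week 8 or Week 16 endoscopy, Section 5.1.1 has the site judge response from the Partial Adapted Mayo score. Section 5.3.1.1 states: "If an endoscopy is completed at an alternative location from the study site the study required biopsy is not required".

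**The concern.** Clinical remission needs SFS, RBS and endoscopy to be good in the same subject. Histologic-endoscopic mucosal improvement and mucosal healing need endoscopy and Geboes to be good together. If a missing component is drawn without its observed companions, the draw keeps the arm-and-stratum average but loses the within-subject association. A subject whose diary shows symptom remission then gets an endoscopic score typical of the whole cell, including subjects who still have symptoms.

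The SAPs justify multiple imputation by a missing-at-random argument and aim at reliable estimates of effect. Random missingness does not protect a composite whose parts are drawn apart. The primary endpoint of each Phase 3 substudy is affected for its COVID-missing share, and HMI is affected for everyone it imputes.

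**Working it through.** **The plan's own figures.** Exact two-sided Fisher power:
- Substudy 3 (12% v 40%, 150 per arm, alpha 0.025): 99.97%.
- Substudy 2 (5% v 18%, 154 placebo and 308 active, alpha 0.05): 98.9%.

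Both agree with the stated figure of more than 95%. The documents give no COVID-missing fraction and no correlation between components.

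**Mechanism.** Within one arm and stratum, let S be observed symptom remission and E an endoscopic subscore of 0 or 1. The true rate is P(S and E). If E is drawn without S, the imputed rate is P(S) × P(E). The shortfall, P(S and E) − P(S)P(E), is the within-cell covariance of S and E. It is positive whenever the two are positively related, and zero if they are unrelated.

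**Simulation.** There were 200,000 subjects per arm. Ordinal SFS, RBS and endoscopic scores came from a shared latent severity, calibrated to the SAP remission rates. Missingness was completely at random. Missing scores were drawn by linear regression with normal residuals, rounded and held to 0–3. Assumptions not in the documents: inter-component latent correlation 0.3, 0.5 or 0.7; COVID-missing fraction 2%, 5% or 10%; Week 0 to Week 52 latent correlation 0.4. Simplifications: integer diary scores, and Week 0 remission as the only stratum (Substudy 3).

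Remission rate among imputed subjects, active/placebo:

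| Case | corr. 0.3 | corr. 0.5 | corr. 0.7 |
|---|---|---|---|
| Substudy 3 (truth 0.40/0.12), endoscopy missing, own-component model | 0.354/0.085 | 0.323/0.066 | 0.286/0.048 |
| same, companions SFS and RBS added | 0.395/0.122 | 0.394/0.127 | 0.400/0.123 |
| Substudy 3, all three missing, own-component models | 0.260/0.052 | 0.231/0.036 | 0.190/0.024 |
| Substudy 2 (truth 0.18/0.05), endoscopy missing, own-component model | 0.134/0.029 | 0.103/0.019 | 0.076/0.011 |
| same, companions added | 0.177/0.053 | 0.172/0.050 | 0.167/0.049 |
| Substudy 2, all three missing, own-component models | 0.092/0.016 | 0.064/0.009 | 0.040/0.004 |

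The Substudy 3 companion row also contains the Week 0 endoscopic score. Adding that score alone moved the imputed rates by at most 0.003, so the recovery comes from SFS and RBS.

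**Effect on the treatment difference.** With missing fraction m, planned rate r and imputed rate x, the arm rate is (1 − m)r + m·x. The difference therefore changes by m × [(x_a − r_a) − (x_p − r_p)].
- Substudy 3, endoscopy missing, correlation 0.5, m = 0.10: active 0.9 × 0.40 + 0.1 × 0.323 = 0.3923; placebo 0.9 × 0.12 + 0.1 × 0.066 = 0.1146; difference 27.77 points against 28.
- Substudy 3, worst case (all three missing, correlation 0.7, m = 0.10): 0.1 × [(0.190 − 0.40) − (0.024 − 0.12)] = −0.0114, giving 26.86 points.
- Substudy 2, worst case: 0.1 × [(0.040 − 0.18) − (0.004 − 0.05)] = −0.0094, giving 12.06 points against 13.

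| Difference in points, m from 2% to 10% | endoscopy only missing | all three missing |
|---|---|---|
| Substudy 3 (planned 28.0) | 27.98 to 27.58 | 27.86 to 26.86 |
| Substudy 2 (planned 13.0) | 12.95 to 12.35 | 12.89 to 12.06 |

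Power by normal approximation stays at or above 99.9% and 98.1%. For scale, NRI-NC at m = 0.10 gives 0.9 × 28 = 25.2 and 0.9 × 13 = 11.7 points.

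**Not simulated:** the histologic composites, the joint model when all three components are missing, and HMI. For the composites the covariance argument gives the direction only.

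**The case against.** The strongest reply is that the SAPs never say companions are excluded. Separate seeds do not rule out sequential imputation in table order. The Table D-2 note explains why MCMC is not needed; it does not list predictors. Substudy 2 Table D-1 does carry an endoscopy MCMC seed, though the Week 16 endoscopy in Part 2 could account for that. A short stretch of the paragraph is redacted. These points lower the certainty, but the reading survives. The predictors are introduced as the variables to be included, no companion appears among them, and the list itself is not redacted.

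The reply is also right about size. The shift is towards the null. NRI-NC and the as-observed analysis use no imputation model, and NRI-NC is more conservative than the effect described here. Wider COVID endoscopy windows also reduce the missing share.

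Two stronger readings are tempting and are not supported:
- A reader might infer that the Substudy 3 model ignores the Week 0 endoscopy. The SAP defines Baseline otherwise: "The induction baseline (thereafter referred to as Baseline) visit date is the date when the first dose of study drug is received during Induction Studies". On that definition, the Week 0 endoscopy can count as a post-baseline measurement. Week 0 clinical remission, which requires an endoscopic subscore of 0 or 1, is a listed predictor. Substudy 3 Table D-2 also gives endoscopy an MCMC seed, which is compatible with a Week 0 value in the model.
- A reader might then infer a sizeable bias in ranked secondary endpoint 4, endoscopic improvement among those with endoscopic improvement at the end of induction. That would follow only if Week 0 endoscopy were left out, so no magnitude is claimed.

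**Conclusion.** The point holds in a limited form. As written, the Phase 3 SAPs impute each component from treatment, strata and its own measurements. Given positive within-cell correlation, COVID-imputed composites are then achieved too rarely in both arms. Among imputed subjects the shortfall is material: in Substudy 3 with endoscopy alone missing, active-arm remission is 0.29 to 0.35 against 0.40.

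Under NRI-C the treatment difference falls by under 0.1 to about 1.1 points in Substudy 3, and by under 0.1 to about 0.9 points in Substudy 2. This is conservative and leaves the power conclusions intact. It rests on the assumed correlation of 0.3 to 0.7 and COVID-missing fraction of 2% to 10%. It would be wrong to infer that the primary conclusions are threatened or that the bias is an established fact.

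The more practical consequence is for HMI. It imputes a wider group, most clearly in Substudy 3, where it covers missing Week 52 evaluations and discontinuations for reasons other than lack of efficacy or adverse events. Imputed rates that are too low pull HMI towards non-responder imputation, so agreement between the two is weaker evidence of robustness than it appears. No figure for HMI was derived.

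**What to change.** In Section 8.3.1 and Appendix D of both Phase 3 SAPs, replace the per-component models with one joint model, or a stated sequence in which companions are predictors. Use it for NRI-C and HMI. Include all same-visit components (SFS, RBS, endoscopic subscore, Geboes) and SFS and RBS from earlier visits, alongside the predictors already listed. For Substudy 3, state explicitly that the Week 0 endoscopic and Geboes scores are in the model, so that two programmers would build the same one.

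The cost is SAP wording and PROC MI code; every variable is already collected. The model is slightly larger and may need convergence checks.

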Part 2 is an open label, 8-week Extended Treatment Period for subjects who did not achieve clinical response at Week 8 in Part 1. The objectives of Part 2 are to offer upadacitinib induction treatment to placebo clinical non-responders (defined by Adapted Mayo Score) from Part 1, and to evaluate delayed clinical response to upadacitinib in subjects who do not initially respond to upadacitinib during Part 1.

During COVID-19 pandemic, investigators should make the best effort to perform the endoscopies required per protocol. For subjects with missing endoscopy at Week 8/16 when endoscopies cannot be performed due to the COVID-19 pandemic, the site should assess the status of clinical response defined by the Partial Adapted Mayo Score. If the subject is a clinical responder at Week 8/16, the subject may enter Study M14-533 Cohort 1. If the subject is a clinical non-responder at Week 8, the subject may enter Part 2. If the subject is a clinical non-responder at Week 16 the subject will discontinue from the study. A notification should be sent to the TAMD as to the responder status and which part of the program the subject will be going to prior to the transfer taking place.

The blind from Substudy 2 Part 1 will be maintained as these subjects will be assessed simply as non-responders and moved to Substudy 2 Part 2 for further treatment in the study. All eligible subjects entering Part 2 will receive open-label treatment with upadacitinib 45 mg QD for 8 additional weeks (until Week 16).

[figure not shown]
Subjects who achieve clinical response defined by Adapted Mayo Score at Week 8 or Week 16 will be eligible to enroll into Substudy 3. Subjects with missing Week 8 or/and Week 16 endoscopy during the period of COVID-19 pandemic will not be eligible to enter Substudy 3. Subjects who do not achieve clinical response at Week 16 will be discontinued from the study and will not be eligible to enroll in Study M14-533 (long-term extension).

The data collected from subjects in Part 2 will not be part of the primary efficacy analysis for the induction study; descriptive statistics will be used, and the results will be reported separately in the clinical study report.

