- **Histologic Endoscopic Mucosal Improvement:** Endoscopic subscore of 0 or 1 and Geboes score ≤ 3.1 .
- **Mucosal Healing:** Endoscopic score of 0 and Geboes score < 2.0 .

Note: Evidence of friability during endoscopy in subjects with otherwise "mild" endoscopic activity will confer an endoscopic subscore of 2.

For subjects enrolled under the protocol with 44-week maintenance period, the efficacy endpoints at Week 52 will apply at Week 44, as applicable.

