3.2 Secondary Endpoints

The ranked secondary efficacy endpoints under overall type I error control are as follows:

1. The achievement of endoscopic improvement at Week 52;
2. The achievement of clinical remission per Adapted Mayo score at Week 52 among subjects who achieved clinical remission at the end of the induction treatment in the Induction Study;
3. The achievement of clinical remission per Adapted Mayo score at Week 52 and corticosteroid free for ≥ 90 days immediately preceding Week 52 among subjects

who achieved clinical remission at the end of the induction treatment in the Induction Study;

4. The achievement of endoscopic improvement at Week 52 among subjects who achieved endoscopic improvement at the end of the induction treatment in the Induction Study;
5. The achievement of endoscopic remission at Week 52;
6. The achievement of clinical response per Adapted Mayo score at Week 52 among subjects who achieved clinical response at the end of the induction treatment in the Induction Study;
7. The achievement of histologic-endoscopic mucosal improvement at Week 52;
8. Change from Baseline in IBDQ total score at Week 52;
9. The achievement of mucosal healing at Week 52;
10. The achievement of no bowel urgency at Week 52;
11. The achievement of no abdominal pain at Week 52;
12. Change from Baseline in FACIT-F score at Week 52;

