3.2 Secondary Endpoints

The ranked secondary efficacy endpoints for Part 1 under overall type I error control are as follows:

1. The achievement of endoscopic improvement at Week 8;
2. The achievement of endoscopic remission at Week 8;
3. The achievement of clinical response per Adapted Mayo score at Week 8;

4. The achievement of clinical response per Partial Adapted Mayo score at Week 2;
5. The achievement of histologic-endoscopic mucosal improvement at Week 8;
6. The achievement of no bowel urgency at Week 8;
7. The achievement of no abdominal pain at Week 8;
8. The achievement of histologic improvement at Week 8;
9. Change from Baseline in IBDQ total score at Week 8;
10. The achievement of mucosal healing at Week 8;
11. Change from Baseline in FACIT-F score at Week 8.

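### Normal-regression imputation with rounding does not reproduce the 0–3 endoscopic subscore, so NRI-C is slightly biased for endoscopic endpoints in both Phase 3 SAPs; a low-severity point with a cheap fix

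*SAP*

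**What the plan says.** Section 8.3.1 of the Substudy 3 SAP makes NRI-C the primary missing-data method for binary endpoints. Data missing for COVID-19 reasons are multiply imputed; all other missing data count as non-response. After MCMC has produced a monotone pattern, "PROC MI will be used to generate 30 datasets using the regression method". Then: "The imputed post-baseline measurements will be rounded to the same precision as the observed data before the determination of responder status". The Substudy 2 SAP uses the same wording in its Section 8.3.1. Appendix D of both SAPs shows that the subscores are imputed, not the binary endpoint, and lists the endoscopic subscore as 0, 1, 2, 3. The visible text gives no bounds, no rule for negative draws, and no ordinal or matching method.

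The endpoints affected are under type I error control:

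- Endoscopic remission is defined as "Endoscopic subscore of 0". It is ranked second in Substudy 2 ("The achievement of endoscopic remission at Week 8") and fifth in Substudy 3 ("The achievement of endoscopic remission at Week 52").
- Mucosal healing starts from the same criterion ("Endoscopic score of 0 and Geboes score" below 2). It is ranked tenth and ninth respectively.
- Endoscopic improvement (subscore 0 or 1) is ranked first in both, and is also a component of the primary endpoint.

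Protocol Section 5.1.1 provides for the loss of these data: "For subjects with missing endoscopy at Week 8/16 when endoscopies cannot be performed due to the COVID-19 pandemic", the site judges response without endoscopy. In Substudy 2 the imputation has little to work from; a note in Appendix D says "The MCMC procedure is not applicable for imputation of endoscopic subscore, which is collected at Baseline and Week 8 only".

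**The concern.** The regression method draws from a normal distribution with one residual variance for all arms. The endoscopic subscore has four values and can pile up at the ends of its scale. Rounding to an integer keeps the values on the grid but does not make the share in each category right. A share at the edge of the scale, such as exactly 0, is the most exposed.

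Section 8.3 of both SAPs says the aim is a reliable estimate of the effect as it would have been without the pandemic. If the imputed subjects carry a distorted treatment difference, NRI-C misses that aim to a degree set by the COVID-missing share. What is at stake is the accuracy of the estimates for the endoscopic endpoints, not the trial's main conclusion.

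**Working it through.** **The plan's own figure.** The plan gives no figure for imputation bias, for the COVID-missing share or for endoscopic score distributions. The nearest figure is the stated power above 95% for the primary endpoint. Exact two-sided Fisher calculations give 99.97% for Substudy 3 (40% vs 12%, 150 per arm, 0.025) and 98.9% for Substudy 2 (18% vs 5%, 308 vs 154, 0.05). Both statements hold.

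**Assumed distributions (scores 0/1/2/3, %).**

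- Substudy 3: active 25/25/30/20, placebo 8/17/35/40.
- Substudy 2: active 14/22/34/30, placebo 2/8/40/50.

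**Approximation.** Ignore all covariates except treatment. An imputed score is then roughly normal with the arm mean and the pooled SD. It rounds to 0 if it lies between −0.5 and 0.5. It rounds to 0 or below if it is under 0.5, which is the rate if negative draws are set to 0. It rounds to 1 or less if it is under 1.5.

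Substudy 3, two active arms and one placebo arm:

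- Means 1.45 and 2.07; variances 1.1475 and 0.8851.
- Pooled variance (2 × 1.1475 + 0.8851)/3 = 1.060, SD 1.030.
- Active, score 0: Φ((0.5 − 1.45)/1.030) = Φ(−0.92) = 17.8%. If negatives are kept, subtract Φ(−1.89) = 2.9%, giving 14.9%.
- Placebo, score 0: Φ(−1.52) = 6.4%, or 5.7% with negatives kept.

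Substudy 2, allocation 2:1:

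- Means 1.80 and 2.38; variances 1.0400 and 0.5156.
- Pooled variance (2 × 1.0400 + 0.5156)/3 = 0.865, SD 0.930.
- Score 0: Φ(−1.40) = 8.1% vs Φ(−2.02) = 2.2% (7.4% vs 2.1% with negatives kept).
- Score 1 or less: Φ(−0.32) = 37.4% vs Φ(−0.95) = 17.2%, against an assumed 36% vs 10%.

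**Simulation with the full model.** This used 200 trials per scenario, 30 imputations, 10% of final endoscopy scores missing at random, and Bayesian normal regression on treatment, three binary strata and earlier endoscopy. Predictive mean matching used 5 donors. Rates are active vs placebo among imputed subjects; the ranges cover two assumed within-subject correlations.

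| | Assumed | Regression, negatives set to 0 | Regression, negatives kept | Predictive mean matching |
|---|---|---|---|---|
| Substudy 3, score 0 | 25% vs 8% | 18% vs 7% | 15% vs 6% | 24% vs 8–9% |
| Substudy 2, score 0 | 14% vs 2% | 8–9% vs 2–3% | 8% vs 2% | 14% vs 2% |
| Substudy 3, score ≤1 | 50% vs 25% | 52% vs 29–30% | same | 49–50% vs 25–26% |
| Substudy 2, score ≤1 | 36% vs 10% | 37% vs 17–18% | same | 36% vs 10% |

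**Reversal.** Assume 5/50/30/15 on active and 2/28/40/30 on placebo. The approximation gives Φ(−1.30) = 9.7% vs Φ(−1.83) = 3.3% scoring 0, so the difference among imputed subjects grows from 3 to about 6 points. The simulation gave about 10% vs 4%; predictive mean matching gave about 5% vs 2%.

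**Whole-trial effect.** With COVID-missing share m, the difference is (1 − m) × assumed difference + m × imputed difference. The imputed differences, with negatives set to 0, are 17.8 − 6.4 = 11.4 and 8.1 − 2.2 = 5.9 points.

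| Assumed m | 2% | 5% | 10% |
|---|---|---|---|
| Substudy 3, NRI-C (17.0 with none missing) | 16.9 | 16.7 | 16.4 |
| Substudy 3, NRI-NC | 16.7 | 16.2 | 15.3 |
| Substudy 2, NRI-C (12.0 with none missing) | 11.9 | 11.7 | 11.4 |
| Substudy 2, NRI-NC | 11.8 | 11.4 | 10.8 |

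The shift is 0.1–0.6 points. If a rounded −1 does not count as 0, the Substudy 3 shift at 10% is 0.8 points. Fisher power for endoscopic remission in Substudy 3 (0.025 assumed, imputed values treated as observed) goes from 95.5% to 95.3%, 95.0% and 94.5%. In Substudy 2 it goes from 99.8% to 99.6% at m = 10%.

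**Rectal bleeding subscore (RBS), conditional only.** The primary endpoint needs RBS of 0. Its rounding unit is unclear. Protocol Section 8.1.3 makes it a three-day diary average, Appendix D of both Phase 3 SAPs labels it 0, 1, 2, 3, and only the Substudy 1 SAP (Section 6.0) rounds it to one decimal. If half the subjects truly have RBS of 0, normal draws give 39% on an integer grid, 13% on thirds and 4% at 0.1. With negatives set to 0 these become 45%, 28% and 23%.

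**The case against.** The best case against acting is size. The effect on any reported estimate is a fraction of a point. Every distribution and missing share above is an assumption. Randomisation in Substudy 2 ended in May 2020 (Appendix D), so its missing share is probably at the low end. Protocol Section 5.3.1.1 widens the endoscopy windows and allows another facility, which limits the loss. NRI-NC and As Observed analyses are planned for the binary ranked secondaries in both SAPs and do not use this imputation, so strong dependence on it would show. In the main scenarios NRI-C is still closer to the assumed truth than NRI-NC. All of this stands and sets the severity low. It does not remove the bias from the method that carries the type-I-controlled tests.

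A redacted fragment follows the Rubin's-rule sentence in the Substudy 3 SAP. The version history says the confidence-interval derivation was added to Section 8.3.1, so the fragment most likely concerns that, but this cannot be checked.

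A reader might infer three stronger points that the documents do not support:

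- **The primary endpoint is seriously damaged through RBS.** That would need RBS itself to be missing and rounded finely. The unit is not settled, and the diary is kept on a handheld device (Protocol Section 10.3), so RBS may be observed when only the endoscopy is missed.
- **The COVID-19 biopsy waiver in Section 5.3.1.1 shows missing endoscopy scores.** It does not: the endoscopy is done and only the biopsy is omitted.
- **Mucosal healing is biased by a known amount.** It shares the endoscopy criterion, but its Geboes part was not simulated.

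**Conclusion.** The point holds as a cheap improvement of low severity. As written, the imputation gives the wrong share of endoscopic scores at 0, and also at 1 or less, among imputed subjects. For endoscopic remission the treatment difference among them falls from 17 to about 9–11 points (Substudy 3) and from 12 to about 5–6 points (Substudy 2) under the assumed distributions. For the whole trial this is about 0.1–0.6 points at an assumed 2–10% COVID-missing share. Power hardly changes and no primary conclusion is at risk.

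It should not be described as always conservative, because the rare-zero case enlarges the difference. The size rests on the assumed distributions, missingness at random and the assumed share; the mechanism rests only on the wording of Section 8.3.1. For RBS the conclusion is limited to this: if it is missing and rounded to thirds or 0.1, a score of 0 would be strongly under-imputed, and the SAPs do not say which unit applies.

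**What to change.** In Section 8.3.1 of both Phase 3 SAPs, impute the endoscopic subscore by predictive mean matching (REGPMM in PROC MI) at the monotone step, keeping the covariates, the 30 imputations and the seeds. For RBS and stool frequency, either do the same or state the rounding unit and limit imputed values to 0–3, with negative draws set to 0.

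The cost is minor reprogramming and an amendment to each SAP, with no extra data or patient burden. It does change the primary missing-data method in a section already revised once after a regulatory comment, so it needs a short rationale. If the Substudy 2 database is already locked, the change belongs there as a labelled sensitivity analysis. Predictive mean matching is only approximate for RBS: in simulation it gave 35–43% of placebo subjects an RBS of 0 against an assumed 35%.
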